9.12.3 Non-Serious Adverse Event Reporting Requirements

Non-serious adverse events are to be reported on the adverse event CRF.

10 DATA ANALYSIS/STATISTICAL METHODS

10.1 Efficacy Evaluation

All patients who have received a minimum of 2 cycles of study treatment had baseline assessments and at least one on-study tumor assessment following treatment will be considered evaluable for response.

Objective Response Rate (ORR) is defined as the proportion of patients with a Complete (CR) or Partial Response (PR) relative to the total number of evaluable patients. Responses will be defined according to the International Myeloma Working Group response criteria (see Appendix C: Multiple Myeloma Disease Tracking for Myeloma Worksheet).

The best overall response is the best response recorded from the start of treatment until disease progression/recurrence (taking as reference for progressive disease the smallest measurements recorded since the treatment started) or the withdrawal from the study. Stable disease will be considered the best response when observed at least after two months from baseline.

Tumor responses will be analyzed in a descriptive manner. The number and percentage of objective response (CR+PR) will be tabulated by dose level. An ORR may be summarized for the RP2D expansion cohort with the corresponding 95% exact confidence interval.

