- Assess effect of ONC201 in combination with dexamethasone on survival endpoints.

Primary Endpoint

- Overall response rate (ORR) using the International Myeloma Working Group response criteria.

Secondary Endpoints

- Overall safety profile of ONC201 as characterized by type, frequency, severity, timing and relationship to study therapy of adverse events and laboratory abnormalities.
- Effects of ONC201 on pharmacodynamic (PD) markers.
- Effects of ONC201 on survival endpoints (i.e., progression-free survival, time to progression, and duration of response).

Study design

This is a Phase 1/2 open-label study of ONC201 administered orally once every week in combination with dexamethasone to patients with relapsed/refractory multiple myeloma.

In Phase 1 of the study, patients will receive 625 mg ONC201 once every week in combination with dexamethasone using a 3+3 dose escalation design that will evaluate up to 625mg ONC201 weekly with 20mg dexamethasone. Three weeks is defined as a treatment cycle.

Phase 1 of the study will involve a safety cohort of at least 6 relapsed/refractory multiple myeloma patients who will receive ONC201 and dexamethasone.

In Phase 2 of the study, patients will receive 625mg ONC201 once every week. Dexamethasone will be administered at a dose determined in Phase 1. Patients may not cross over from Phase 1. Tumor assessments will be conducted using the International Myeloma Working Group response criteria. The study plans to enroll 42 patients over a period of 2 years.

Eligibility criteria

Inclusion

1. Patients must be refractory to, or not a candidate for, established therapy known to provide clinical benefit for their malignancy.
2. Measurable disease M protein component in serum (at least 0.5 g/dL) and/or urine (if present) (≥ 0.2 g excreted in a 24 hour collection sample), or serum free light chain level ≥ 10 mg/dL, provided the serum free light chain ratio was abnormal.
3. Able to swallow and retain oral medication.
4. All previous therapies for cancer, including radiotherapy, major surgery and investigational therapies discontinued for ≥ 14 days (≥ 28 days for mitomycin C or nitrosoureas) before study entry, and all acute effects of any prior therapy resolved to baseline severity or Grade ≤ 1 Common Terminology Criteria for Adverse Events (CTCAE v4.03), except alopecia or parameters defined in this eligibility list.
5. Age ≥ 18 years.
6. ECOG performance status ≤ 1 .

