7. Solitary bone or solitary extramedullary plasmacytoma as the only evidence of plasma cell dyscrasia.
8. Subjects with serum calcium (corrected for albumin) $\geq 12 \text{ mg/dL}$
9. Any of the following in the previous 6 months: myocardial infarction, severe/unstable angina, coronary/peripheral artery bypass graft, symptomatic congestive heart failure, cerebrovascular accident, transient ischemic attack or symptomatic pulmonary embolism.
10. Other severe acute or chronic medical or psychiatric condition or laboratory abnormality that may increase the risk associated with study participation or study drug administration, or may interfere with the interpretation of study results, or in the judgment of the investigator would make the patient inappropriate for entry into the study.
11. Actively receiving medications that have the risk of Torsades de Pointes or are strong cytochrome P450 inhibitors or inducers.

Statistical methods

Overall response rate (ORR) will be determined with the corresponding 95% exact confidence interval. Descriptive statistics will be provided for selected demographic, safety, PD and biomarker data by dose, dose schedule and time, response rate, and time to progression as appropriate. Descriptive statistics on continuous data will include means, medians, standard deviations, and ranges, while categorical data will be summarized using frequency counts and percentages.

SCHEDULE OF ACTIVITIES

Table 1: Schedule of Activities

Examination ¹	Baseline	Cycle 1				Cycle 2	Cycle 3+	Follow up ²
Day	-28	1	2& 3	8	15	1	1	1
Informed Consent	X							
Medical History	X							
Inclusion/Exclusion Criteria	X	X						
Concurrent meds	X	X				X	X	X
Physical exam³	X	X				X	X	X
Performance Status (ECOG)	X	X						
Vital signs⁴	X	X				X	X	X
Pregnancy Test	X							
Urinalysis	X	X				X	X	
Toxicity Assessment⁵	X	X		X	X	X	X	X
12-Lead EKG⁶	X	X			X	X		
Bone Marrow Aspiration/Biopsy⁷	X			X			X ⁷	X ⁷
Serum Protein Electrophoresis	X	X				X	X	X

¹All assessments have a ± 2 business day window, except where specified.

²4 weeks (28 days) after off study visit.

³Height (baseline only) and weight included.

⁴Blood pressure, HR, temperature and respiratory rate.

⁵Toxicity assessments will be performed at each patient encounter. Baseline signs and symptoms prior to C1D1 must also be assessed.

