1.3 Clinical Studies

The clinical safety of ONC201 has been evaluated in a phase I clinical trial. The design was an open-label, dose-escalation phase I trial of monoagent ONC201 in patients with advanced, refractory tumors who had exhausted or refused standard treatment options for their respective indications. The primary objective of this study was to determine the recommended phase 2 dose (RP2D) of ONC201 administered orally in patients with advanced cancers, as well as to evaluate the safety and tolerability of the drug. Secondary objectives included pharmacokinetics

CONFIDENTIAL

and pharmacodynamics evaluation of ONC201 and preliminary assessment of anti-tumor efficacy.

An accelerated dose escalation design was employed to reduce the number of patients treated at potentially sub-therapeutic dose and to accelerate the determination of the recommended phase 2 dose. Ten evaluable patients (aged 47-80 years) received oral ONC201 once every 3 weeks at five dose levels ranging from 125 to 625 mg. The study design included only one patient per cohort until any patient experiences a grade 2 adverse event during the first cycle of treatment, defined as 21 days. Five dose levels (125 mg, 250 mg, 375 mg, 500 mg, 625 mg) were selected for the study. Enrollment at each subsequent dose level required that all patients enrolled at the prior dose level completed Cycle 1 dosing and were evaluated 21 days later to assess safety.

On average, patients received 2.9 doses of ONC201. Nine out of ten patients completed at least 2 cycles, 4 patients completed at least four cycles, and one patient received six cycles and remains on therapy. 625 mg was the highest dose administered and was determined to be the RP2D. Dyspnea and fatigue was observed in a few patients, which was attributed to their underlying disease. No drug-related toxicities Grade >1 were observed in any patients in this study.

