3.2 Number of Patients

Phase 1 is expected to enroll up to 12 patients and Phase 2 will enroll up to 30 evaluable patients over the course of 2 years. The actual sample size will depend on the clinical results.

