5.5 Criteria for Removal from Study

In the absence of treatment delays due to adverse event(s), treatment may continue until one of the following criteria applies:

- Disease progression
- Intercurrent illness that prevents further administration of treatment \geq 14 days or specific changes in the patient's condition that render the patient unacceptable for further treatment in the judgment of the investigator
- Patient non-compliance with protocol requirements (determined via meeting with PI, applicable Sub-I, clinical research coordinator, and patient)
- Unacceptable adverse event(s). Note, a DLT in and of itself may not be an unacceptable adverse event. However, any grade 4 study-drug related AE is unacceptable and will lead to withdraw. The investigator will use his/her opinion, in consultation with the PI, to determine if a study-drug related AE is unacceptable, acceptable, or clinically insignificant (also acceptable).
- Withdrawal of consent (attempts should be made to clarify, with the patient, if withdrawal is specific to study participation, or if it applies to data collection as well). Note: patients lost to follow up (defined as no contact $>$ 60 days after last on-study contact and at least 3 attempts) are considered to have withdrawn study participation consent. Data collection is permissible. Date of last contact will be recorded as the withdrawal date.
- Pregnancy
- Oncoceutics' decision to forgo further drug development of ONC201

The reason for study removal and the date the patient was removed must be documented in the CRF.

Severe adverse events, availability of new adverse toxicology in animals, and financial difficulties due to withdrawal of funds may result in stopping the trial. An investigator, Sponsor, or IRB may take such actions. If the trial is terminated for safety reasons, subjects will be notified immediately and assured that appropriate treatment and follow-up will be available. If an investigator terminates the trial he will inform the Sponsor, subjects, and IRB about the reason for such action. Similarly if the Sponsor terminates the trial, it will inform the investigators, the IRB, and the subjects of the reason for such an action. Similar notifications will be sent by the IRB if it takes such an action.

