7.2 Trials Period

The following procedures/assessments will be performed on the days specified in the Schedule of Activities:

- Vital signs
- Weight
- ECOG performance status
- Physical exam
- Hematology, blood chemistry, coagulation, urinalysis, and per SoA
- Triplicate EKG (12 leads)
- Study drug compliance
- Adverse events
- Drug compliance
- Concomitant medications
- Tumor assessment: at the end of every even cycle (e.g., Cycles 2, 4, 6)
- Blood draws for PK/PD
- Urine collection

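### The primary ORR counts only patients with at least 2 cycles of treatment, so earlier failures leave the denominator, and no all-treated ORR is planned

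*Combined protocol and SAP*

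**What the plan says.** ORR by International Myeloma Working Group criteria is the only primary endpoint (Section 2.2.1). Section 10.1 sets the analysis population: "All patients who have received a minimum of 2 cycles of study treatment had baseline assessments and at least one on-study tumor assessment" after treatment are evaluable. It defines ORR as CR plus PR "relative to the total number of evaluable patients". A cycle is 21 days (Section 3.3), so the entry condition is about 6 weeks of treatment.

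Sections 5.5 and 7.6 both say that "treatment may continue until one of the following criteria applies", and the criteria include progression and unacceptable adverse events. The first scheduled tumor assessment is at the end of cycle 2 (Section 7.2). Section 8.2 adds assessments when progression is suspected and at withdrawal.

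The population is described differently from section to section:

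- Section 3.2: "Phase 2 will enroll up to 30 evaluable patients".
- Section 8.2: the 10% and 30% rates are set for patients given ONC201, and the 84% power is attached to 30 patients enrolled.
- Section 10.2: the futility trigger is stated in enrolled patients.
- Synopsis: an exact 95% interval for ORR, with no denominator named.

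No section plans an all-treated ORR. Intention to treat appears only in the abbreviation list (Appendix A).

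**The concern.** Whether a patient enters the denominator depends on the patient's outcome. Early progression, death and early toxicity are the main ways of failing to complete 2 cycles, and such patients are unlikely to be responders. Section 8.2 may have a progression formally documented in week 4, yet Section 10.1 leaves that patient out of the rate. Nothing in the plan puts the patient back as a non-responder.

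The trial has a single arm, so no control group shares the bias. The estimate is compared with a fixed 10% background rate, and interest in further development depends on it. If the 10% and 30% describe everyone treated while the observed rate describes only those who stayed about 6 weeks, the comparison mixes two populations. The reader also cannot tell which patients the 84% power refers to.

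**Working it through.** **Inputs from the documents.** Null rate 0.10, target rate 0.30, one-sided alpha 0.05, 30 patients, stated power 84% (Section 8.2). Denominator: evaluable patients (Section 10.1).

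**Inputs assumed.** q is the share of treated patients who are not evaluable. The documents do not give it, so 10%, 20% and 30% are shown. r is the response rate among excluded patients, set to 0 unless stated. The success cutoff is also not stated and is inferred in step 1.

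**1. The plan's own figure.** With X ~ Binomial(30, p), the smallest cutoff with type I error of at most 0.05 is 7:

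- P(X ≥ 6 | 0.10) = 0.073, too large.
- P(X ≥ 7 | 0.10) = 0.026.
- P(X ≥ 7 | 0.30) = 0.840, which reproduces the stated 84%.

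The power arithmetic is right for 30 patients in the analysed set. The issue is which patients those are.

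**2. Who leaves the denominator.** A patient who stops before completing 2 cycles fails the Section 10.1 condition whatever was documented. A patient who completes cycle 2 and progresses at the assessment that ends it has met the condition and counts as a non-responder. The loss is therefore confined to failures before 2 cycles are complete.

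**3. Effect on the estimate.** To obtain 30 evaluable patients, 30/(1 − q) must be treated (rounded to the nearest whole patient). With r = 0, the all-treated ORR is the evaluable ORR × (1 − q).

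| q (assumed) | 30/(1 − q) | Evaluable ORR | All-treated ORR | Difference |
|---|---|---|---|---|
| 10% | 33.3 | 7/30 = 23.3% | 7/33 = 21.2% | 2.1 points |
| 20% | 37.5 | 7/30 = 23.3% | 7/38 = 18.4% | 4.9 points |
| 30% | 42.9 | 7/30 = 23.3% | 7/43 = 16.3% | 7.1 points |

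The ratio 1/(1 − q) is the overstatement at r = 0. It is smaller if some excluded patients respond, which is possible: Table 1 schedules "Serum Protein Electrophoresis" at cycle 2 day 1, so an early fall in M-protein could be seen.

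**4. Type I error, under stated conditions only.** Suppose 10% is an all-treated rate, losses are replaced until 30 are evaluable, and the cutoff is 7. The evaluable rate under the null is then (0.10 − q·r)/(1 − q).

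| q (assumed) | Evaluable rate, r = 0 | P(X ≥ 7), r = 0 | Evaluable rate, r = 5% | P(X ≥ 7), r = 5% |
|---|---|---|---|---|
| 10% | 0.111 | 4.3% | 0.106 | 3.4% |
| 20% | 0.125 | 7.3% | 0.113 | 4.5% |
| 30% | 0.143 | 12.6% | 0.121 | 6.4% |

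The 5% level is passed only beyond q = 13% (r = 0) or q = 23% (r = 5%). If exactly 30 are treated and the cutoff stays at 7, type I error remains 2.6%. There is also no inflation if 10% is itself an evaluable-patient rate with similar loss.

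**5. Power if all 30 treated are analysed.** If 30% is an all-treated rate, power is 84%, as now. If 30% is an evaluable-patient rate and r = 0, the all-treated rate is 0.30 × (1 − q), that is 0.27, 0.24 or 0.21. P(X ≥ 7) is then 74%, 60% or 45%.

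**The case against.** The strongest reply is that the loss is narrow and its size unknown. Progressors at the first scheduled assessment are kept. Section 6 allows holds and dose reductions, so not every toxicity ends treatment early. A shift of 2.1 points at q = 10% is small beside the exact 95% interval for 7/30 (9.9% to 42.3%), and Section 10.1 calls the response analysis descriptive. All of this stands, and it limits what can be said about size. It does not change the direction, and it does not supply the missing all-treated rate.

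Four stronger readings are tempting, and the documents do not support them.

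- **A loss rate of 10%.** Section 1.3 reports "Nine out of ten patients completed at least 2 cycles" in the earlier trial, and a reader might take q = 10% from it. That section describes the ten as evaluable already, so the figure does not estimate loss among treated patients.
- **A futility table that often gives opposite decisions.** Section 10.2 states its trigger twice in enrolled patients. The word evaluated occurs only in the credible-interval illustration. A conflict arises only if the Section 10.1 population is carried into Table 10.1, and at 12 enrolled it also needs zero responses. With q = 10% assumed and no responses among the excluded, the chance of zero responses with at least one of the 12 not evaluable is 0.9^12 − 0.8^12 = 21% at a true all-treated ORR of 10%, and 0.7^12 − 0.6^12 = 1.2% at 30%. What remains is a mismatch of terms between Sections 10.1 and 10.2.
- **An established inflation of type I error.** It needs every condition in step 4 of the working, and the documents permit readings with none.
- **Too few places to reach 30 evaluable.** The Synopsis says "The study plans to enroll 42 patients over a period of 2 years", which is a plan and not a cap. Phase 1 need not use all 12 places, and Section 3.2 gives 30 as an upper limit.

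Evaluable-only rates are common as supportive analyses in phase 2. Here it is the only ORR planned.

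**Conclusion.** The concern holds for the denominator. Followed as written, Section 10.1 removes failures before 2 cycles from the primary ORR, and no planned analysis counts them as non-responders. The resulting rate overstates the ORR among patients given ONC201, which is the quantity Section 8.2 uses for its decision. That direction assumes only that excluded patients respond less often than retained ones, which is reasonable for early progressors and deaths.

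The size rests on an assumed q. If no excluded patient responds, 23.3% among evaluable patients becomes 21.2%, 18.4% or 16.3% among treated patients at q = 10%, 20% or 30%. The documents support neither a particular q nor a general statement that the type I error exceeds 5%. Sections 3.2, 8.2, 10.1 and 10.2 do not share one population, and that needs correcting whatever the size of the bias.

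**What to change.** - In Section 10.1, define the primary Phase 2 ORR over all patients who receive at least one dose of ONC201. Count anyone without a documented CR or PR as a non-responder, including those with no post-baseline assessment.
- Keep the 2-cycle evaluable ORR as a supportive analysis.
- Use the same population in Sections 3.2, 8.2, 10.1 and 10.2. For futility, count a patient once assessed or off treatment.
- State and justify which population the 10% and 30% rates describe, and state the success cutoff.

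The cost is wording in four sections, a somewhat lower reported ORR, and possibly a lower stated power. Power stays at 84% with 30 treated if 30% is an all-treated rate. If it is an evaluable-patient rate, power must be restated: 74%, 60% or 45% at assumed q of 10%, 20% or 30%. The Phase 2 maximum of 26 in Table 10.1, against 30 in Sections 3.2 and 8.2, is a separate inconsistency to settle before the cutoff is fixed.

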10.2 Futility Analysis

A Bayesian method by Thall et al (1995) will be used for futility monitoring in Phase 2 of the study. The trial will be stopped early if $\Pr(\text{ORR} < 0.1 | \text{data}) > 0.95$. That is, the trial will be stopped early if there is more than a 95% probability that the ORR is lower than 10%. We assume that ORR follows a prior distribution of beta (0.1, 0.9).

The futility rules will be implemented once the first 12 patients have been enrolled in Phase 2. The corresponding stopping boundaries are listed in the following table 10.1. For example, if there are no responses in the first 12 patients enrolled in Phase 2, the trial will be terminated early due to futility. Multc Lean software V2.1 was used for the design. If the trial continues until 20 additional patients are evaluated, and 3 responses are observed among the 26 patients, then the 95% credible interval for the response rate would be (2.6%, 25.7%).

Table 10.1: Stopping boundaries for futility monitoring

# Patients (inclusive)	Stop the trial if there are this many responses total:

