	# responders (inclusive)
1-11	Never stop with this many patients
12-23	0
24-25	0-1
26	Reach maximum number of patients, always stop

10.3 Early Stopping Rules for Safety/adverse events:

Adverse events will be assessed continuously throughout the study. During evaluation of the first cohort of 12 eligible patients, if 4 patients have to discontinue the study drug due to treatment-related adverse events, the study will be interrupted for consideration of dose reduction or termination. If 6 of a total of 26 eligible patients have to discontinue the study drug due to treatment-related adverse events the study will be suspended and early termination for excess toxicity will be considered after careful investigation of the causes of the higher than expected toxicities. Once the cause of the higher than anticipated toxicities has been determined, the study team will confer with the FCCC DSMC and IRB to make a determination whether accrual can be resumed or the study will be terminated early. The chance of early termination with a true toxicity of 30% is 51%. The chance of early termination in error (when true toxicity is 5%) is 0.2%. The overall study power is 85% (for detection of overly toxic treatment) and has type I error of 0.3%.

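### Table 10.1 stops Phase 2 for futility at 1 response in 24 or 25 patients, but the posterior there is 0.905 to 0.914, short of the 0.95 that the written rule requires

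*Combined protocol and SAP*

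**What the plan says.** Section 10.2 (Futility Analysis) sets a Bayesian futility rule for Phase 2. It gives the rule as a formula and again in words: "the trial will be stopped early if there is more than a 95% probability that the ORR is lower than 10" per cent. The prior is stated: "We assume that ORR follows a prior distribution of beta (0.1, 0.9"). Monitoring has a defined start: "The futility rules will be implemented once the first 12 patients have been enrolled in Phase 2". The section then says that Table 10.1 holds the boundaries that correspond to this rule.

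Table 10.1 reads as follows:

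- 1 to 11 patients: "Never stop with this many patients"
- 12 to 23 patients: stop with 0 responses
- 24 to 25 patients: stop with 0 or 1 responses
- 26 patients: "Reach maximum number of patients, always stop"

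The section also gives a worked example for 3 responses in 26 patients: "then the 95% credible interval for the response rate would be (2.6%, 25.7"%). No other futility cut-off appears in the protocol, and nothing says whether the text or the table prevails.

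**The concern.** The table is offered as the output of the written rule, so each boundary should have a posterior probability above 0.95. A single response in 24 patients is an observed rate of about 4%, and under a prior worth one patient it is doubtful that this gives 95% certainty of a true rate below 10%. If it does not, the protocol gives two binding and opposite instructions for the same data. The choice between them would then be made in an open-label trial, after the responses are known. If the table were followed, the statement that a stop reflects more than 95% certainty would be untrue at that boundary.

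**Working it through.** **Inputs** (all from Section 10.2 and Table 10.1): reference ORR 0.10, cut-off 0.95, prior Beta(0.1, 0.9), monitoring from 12 patients, table maximum 26.

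**Formula.** With x responses in n patients the posterior is Beta(0.1 + x, 0.9 + n − x). The rule compares its distribution function at 0.10 with 0.95.

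**Check on the prior.** For 3 responses in 26 the posterior is Beta(3.1, 23.9). Its 2.5% and 97.5% points are 2.62% and 25.65%, which match the interval printed in the section. The prior is therefore read correctly.

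**Posterior probability that ORR < 0.10:**

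| Responses / patients | Posterior | Rule (> 0.95) | Table 10.1 |
|---|---|---|---|
| 0/12 | 0.9851 | stop | stop |
| 0/23 | 0.9969 | stop | stop |
| 0/24 | 0.9973 | stop | stop |
| 0/25 | 0.9977 | stop | stop |
| 1/23 | 0.8944 | continue | continue |
| **1/24** | **0.9047** | **continue** | **stop** |
| **1/25** | **0.9139** | **continue** | **stop** |
| 2/25 | 0.7034 | continue | continue |

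One response gives 0.9485 at 30 patients and 0.9535 at 31, so it first meets the written rule at 31. From 12 patients onward, the rule as written stops only with 0 responses. The row for 1 to 11 patients is no conflict, because the text starts monitoring at 12.

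**Could the cited method explain the gap?** The method may allow the 10% standard rate to be uncertain. The documents give no such setting, so this is an assumption: a standard rate with mean 10% and a Beta distribution of effective sample size 10 to 10,000.

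| Effective sample size | 1/24 | 1/25 |
|---|---|---|
| 10 | 0.704 | 0.713 |
| 100 | 0.878 | 0.888 |
| 1,000 | 0.902 | 0.911 |
| 10,000 | 0.904 | 0.914 |

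Uncertainty in the standard lowers the posterior, so it does not bring it to 0.95.

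**What would reproduce the table?** A cut-off of 0.90 does so exactly from 12 patients: 1/23 at 0.8944 continues, while 1/24 at 0.9047 and 1/25 at 0.9139 stop.

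**Effect on early stopping.** Assume a look after every patient from 12 to 25, with each response known at the look.

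- By the written rule, the only way to stop is 0 responses in the first 12: (1 − p)^12.
- The table adds the path with exactly 1 response, which must fall among the first 12 patients, and none in the next 12: 12 × p × (1 − p)^11 × (1 − p)^12 = 12p(1 − p)^23.

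| True ORR | Rule | Added by the table | Table |
|---|---|---|---|
| 5% | 54.0% | 18.4% | 72.5% |
| 10% | 28.2% | 10.6% | 38.9% |
| 30% | 1.38% | 0.10% | 1.48% |

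The totals are from unrounded values.

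**The case against.** The arithmetic is not in dispute. The case on the other side is about reach and cause.

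- **Narrow scope.** The conflict is confined to exactly 1 response at 24 or 25 patients. This stands.
- **Small practical effect.** All of the added stopping occurs at patient 24 when every patient triggers a look. Against the table's maximum of 26, such a stop saves two patients. It cannot overturn an efficacy finding at 26: 1/24 can become at most 3/26, while an exact one-sided 5% test of a 10% rate needs 6/26 (tail probability 0.040). At 30 patients it needs 7/30 (0.026), so all six remaining patients would have to respond. This also stands, and the point does not rest on lost power or an inflated type I error.
- **Unknown cause.** A 0.90 cut-off is an inference. Keeping 0.95 and raising the reference rate to roughly 12.5% to 12.9% also fits the 24 to 25 row, since the 95th posterior percentile is 12.46% at 1/24 and 12.96% at 1/23. The software inputs are not given, so neither text nor table can be presumed to be the intended one.
- **Conditional figures.** The protocol does not state how often looks occur. Section 10.2 counts patients enrolled, whereas Section 10.1 requires two cycles and an on-study assessment for a patient to be evaluable. The stopping probabilities depend on the look schedule; the posterior values do not.

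None of this reconciles the rule with the table.

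**Conclusion.** The concern holds. At 1 response in 24 or 25 patients, Table 10.1 orders a stop that the written rule does not permit: the posterior is 0.905 or 0.914, not above 0.95. This follows from the stated prior, reference rate and cut-off alone, and the printed credible interval confirms the prior.

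Under the look schedule assumed above, the chance of reaching the contradiction is about 1 in 9 (10.6%) if the true ORR equals the 10% background rate, 18.4% at 5%, and 0.1% at 30%. It mainly concerns an inactive regimen and barely touches power. It must still be corrected, because a binding stopping rule cannot give two answers to the same data.

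**What to change.** The sponsor should confirm from the design file which cut-off was intended, and then do one of the following:

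1. State the rule in Section 10.2 as Pr(ORR < 0.1 | data) > 0.90. Table 10.1 then stands as printed from 12 patients on. The cost is 0.1 percentage point more early stops at an ORR of 30%.
2. Keep 0.95 and change the 24 to 25 row to 0 responses. The cost is fewer early stops for an inactive regimen (28.2% instead of 38.9% at an ORR of 10%).

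In either case, print the posterior probability beside each boundary and say how often the rule is applied.

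The edit is one number or one row, needs no extra patients, and should be made before monitoring reaches 24 patients. A separate matter bears on the regenerated table: it ends at 26, while Sections 3.2 and 8.2 plan 30 Phase 2 patients. If 30 is kept, rows for 26 to 29 are needed. They would be 0 responses under 0.95 (1/29 gives 0.943) and 0 or 1 under 0.90 (1/26 gives 0.922; 2/29 gives 0.780).
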